#### 2.8.4.2 Vital signs

Vital sign assessments are performed in order to characterize basic body function. The following parameters were collected: height (cm), weight (kg), body temperature (°C), pulse rate, systolic and diastolic blood pressure (mmHg).

#### Data handling

Vital signs collected on treatment will be summarized. Values measured outside of on treatment period will be flagged in the listings.

#### Data analysis

For analysis of vital signs the clinically notable vital sign criteria are provided in [Table 2-2](#) below.

**Table 2-2 Clinically notable changes in vital signs**

Vital sign (unit)	Clinically notable criteria	
	above normal value	below normal value
Weight (kg)	increase > 10% from baseline	decrease > 10% from baseline
Systolic blood pressure (mmHg)	>=180 with increase from baseline of >=20	<=90 with decrease from baseline of >=20
Diastolic blood pressure (mmHg)	>=105 with increase from baseline of >=15	<=50 with decrease from baseline of >=15
Pulse rate (bpm)	>=100 with increase from baseline of >25%	<=50 with decrease from baseline of > 25%
Body temperature (°C)	>= 39.1	-

The number and percentage of subjects with notable vital sign values (high/low) will be presented.

In addition, values and change from baseline of vital signs will be summarized at each visit by descriptive statistics including mean, SD, median, 25th and 75th percentiles, minimum, and maximum.

A listing of all vital sign assessments will be produced and notable values will be flagged. In the listing, the assessments collected outside of on-treatment period will be flagged.

### 2.8.4.3 Bone Marrow Examination

Following bone marrow examination data will be listed.

- Bone marrow aspiration
- Bone marrow biopsy
- Chromosomal test (Karyotype and FISH)
- Peripheral blood smear test

## 2.9 Pharmacokinetic endpoints

PAS will be used in all pharmacokinetic data analyses and PK summary statistics. In the case of samples taken are not within the time windows around the scheduled time points. These samples will exclude from the descriptive statistic which are summarized by time point, but will include in the non-compartmental PK analysis.

### PK parameters for subjects with intensive PK samples

The PK parameters that will be determined are shown in [Table 2-3](#). PK parameters of eltrombopag, including but not limited to those listed in [Table 2-3](#), will be calculated from the individual concentration-time profile obtained following the administration of the study treatment and listed by subject.

**Table 2-3 Non-compartmental PK parameters**

AUClast	The AUC from time zero to the last measurable concentration sampling time (tlast) (mass*time*volume  )
AUCtau	The AUC calculated to the end of a dosing interval (tau) at steady-state (amount*time*volume  )
Cmax	The maximum (peak) observed plasma drug concentration after dose administration (mass*volume  )
Tmax	The time to reach maximum (peak) plasma drug concentration after dose administration (time)
Ctrough	Pre-dose concentration at the end of dose interval (mass*volume  )
CLss/F	Apparent systemic (or total body) clearance at steady state from plasma (volume/time)

Descriptive statistics (n, arithmetic mean, CV% mean, standard deviation (SD), median, geometric mean, CV% geo-mean, minimum and maximum) will be presented for all PK parameters defined above except Tmax, where only n, median, minimum and maximum will be presented.

### PK concentrations

Descriptive statistics including mean (arithmetic and geometric), SD, CV (arithmetic and geometric), median, minimum and maximum for plasma eltrombopag concentration will be

presented by dose, visit/sampling time point, including the frequency (n, %) of concentrations below the LLOQ and reported as zero.

For subjects with intensive PK samples, the geometric mean and arithmetic mean (SD) concentration-time profiles will also be graphically presented. In addition, individual concentration-time profiles will be displayed graphically.

In addition, plasma eltrombopag concentrations for subjects with sparse PK samples will be summarized by dose, visit and scheduled time point.

All individual plasma eltrombopag concentration data will be listed by dose, visit and scheduled time point.

### **Handling of PK data below LLOQ or missing**

All concentration values below the lower limit of quantitation (LLOQ) are set to zero by the Bioanalyst, and will be displayed in the listings as zero and flagged. LLOQ values will be treated as zero in any calculations of summary statistics, and treated as missing for the calculation of the geometric means and their CV%. The number of non-zero concentrations will also be reported in the summary statistics.

Missing values for any PK data will not be imputed and will be treated as missing.

### **Subgroup analyses for the pharmacokinetic endpoint**

The pharmacokinetic endpoint will be summarized by the above subgroups listed in [section 2.2.1](#).

## **2.10 PD and PK/PD analyses**

If data permits, PK/PD and exposure-response analyses may be explored in a separate report.

## **2.11 Patient-reported outcomes**

There will be no patient-reported outcome analysis planned in this study.

## **2.12 Cytogenetic abnormalities and clonal evolution**

### **Cytogenetic abnormalities and clonal evolution observed during the study**

Cytogenetic abnormalities and clonal evolution will be selected from AE page in eCRF, and will be chosen as AE Preferred term = “clonal evolution / cytogenetic abnormality / AML / MDS / PNH”.

Clonal cytogenetic evolution will be evaluated during the study, and the rate of the subjects who developed any clonal evolution (e.g., clonal evolution to PNH, evolution to AML or MDS etc.) will be calculated in a summary table. Short narratives and relevant information for subjects with new cytogenetic abnormalities on study will be listed.

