This is a non-randomized, open label, single arm, multi-center, Phase II study to evaluate the efficacy and safety of eltrombopag in combination with IST regimen of r-ATG + CsA in East-Asian patients with SAA who have not received prior IST. At least 36 participants will be enrolled from China, Japan, Korea or Taiwan. At least 6 pediatric participants will be recruited in total, with 3 participants from China and 3 from Japan respectively. At least one of the 6 pediatric participants in each age group (6 to 11 years old, and 12 to 17 years old) will be enrolled. For the 30 adult participants, at least 12 participants will be recruited from China to fulfill the requirements for pharmacokinetic (PK) profile.

Figure 3-1 Study design

Eligible participants will be enrolled into the study and will receive eltrombopag (from Day 1 to Week 26) concomitantly with r-ATG (on Days 1-5) and CsA (from Day 1 to Week 26) in the core treatment part.

Efficacy assessments will be performed at Week 13 and Week 26 in the core treatment part of the study.

Participants who are assessed as responders (meeting CR or PR criteria) at Week 26 are eligible to the extension part of the study and continue treatment with eltrombopag and CsA after Week 26.

Study treatment should be discontinued if the participant is not assessed as a responder at Week 26.

During the extension part, eltrombopag treatment will be provided up to Week 52. CsA will be maintained or tapered at the investigator's discretion according to local practice, with a total duration of at least 2 years (18 months after Week 26, see [Section 6.1.5](#)). End of treatment (EOT) assessments will be performed after eltrombopag discontinuation at anytime during the study. After that, safety follow-up visit will be performed 30 days after the discontinuation of eltrombopag, and participants will enter the long-term follow-up part, with yearly efficacy and clonal evolution assessments up to Year 3 (Week 156).

For non-responders at Week 26, and participants who relapse or receive alternative SAA treatment, safety follow-up visit will be performed 30 days after the discontinuation of eltrombopag, and then clonal evolution and survival will continue to be followed up to Year 3 (Week 156).

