Adverse Events	X	X	X	X	X	X	X	X	X	X	X	X	X	X	X			
CsA level			X	X	X	X	X	When clinically indicated	X	X	X	When clinically indicated	X	If clinically indicated				
Hematology	X	X	X	X	X	X	X	X	X	X	X	X	X	X			X	
Peripheral blood smear	X	X	X			X		Every 4 weeks		X	X	Every 4 weeks	X	X	X			X
Blood coagulation test (PT/INR and aPTT)	X	X			Perform when clinically indicated (e.g., TEE suspected)											If clinically indicated	If clinically indicated	
Clinical Chemistry	X	X	X	X	X	X	X		X		X	X	X	X	X			

Period	Screening	Core treatment part											Extension part		EOT		Long-term Follow-up	
		Screening	Day 1	Week 1	Week 2	Week 3 / 5 / 7	Week 4 / 8	Week 6	Week 9/11/15/17/19/21/23/25 when dose adjusted	Week 10/12/14/16/18/20/22/24	Week 13	Week 26	Week 28 to Week 50 ¹	Week 52	End of treatment	Safety follow-up	Survival follow-up	Year 2 / Year 3
Visit Name	Screening																	
Days	-30 to -1	1	8	15	22 / 36 / 50	29 / 57	43	64 to 176	71 to 169	92	183	197 to 351	365	EOT	30 days after EOT	every 3 months	729 / 1093	
Bone marrow aspiration (iliac crest) and cytogenetic analysis	Within 30 days of Day 1												X	X	X	Not necessary if conducted within 3 months.		X
Flow cytometry of CD34 positive cells from bone marrow aspiration	Within 30 days of Day 1												X	X	X	Not necessary if conducted within 3 months		X
Bone marrow biopsy	Within 30 days of Day 1												X	X	X	Not necessary if conducted within 3 months.		X
FISH	Within 30 days of Day 1												X	X	X	Not necessary if conducted within 3 months		X

Period	Screening	Core treatment part												Extension part		EOT		Long-term Follow-up	
		Screening	Day 1	Week 1	Week 2	Week 3 / 5 / 7	Week 4 / 8	Week 6	Week 9/11/15/17/19/21/23/25 when dose adjusted	Week 10/12/14/16/18/20/22/24	Week 13	Week 26	Week 28 to Week 50 ¹	Week 52	End of treatment	Safety follow-up	Survival follow-up	Year 2 / Year 3	
Visit Name	Screening																		
Days	-30 to -1	1	8	15	22 / 36 / 50	29 / 57	43	64 to 176	71 to 169	92	183	197 to 351	365	EOT	30 days after EOT	every 3 months	729 / 1093		
Pregnancy test (serum or urine)	Serum test (S)	Urine test (S)					Urine test (S)		Urine test once a month (S)			Urine test (S)	Urine test (S)	Urine test once a month (S)	Urine test (S)	Urine / Serum test (S) ⁴	Serum test (S)	Urine test monthly till 1 month after CsA stop(S)	Serum test at Year 3 (S)
Chest X-ray	X																		
Abdominal sonography	X																		
Echocardiogram	X																		

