8.4.3 Bone marrow aspiration and biopsy

Bone marrow aspirate for morphology, proportion of blasts, dysplasia, cytogenetics (karyotype analysis with G-banding and FISH), and for CD34 positive cells; bone marrow biopsy for cellularity, degree of fibrosis (reticulin stain and collagen stain), and dysplasia will be sampled during Screening, Week 13, Week 26, Week 52 and yearly after according to the schedule of assessments and collection plan outlined in [Table 8-1](#).

If the site laboratory is unable to perform the test (i.e., due to quality/sampling issue with the sample), particularly for cellularity and chromosome abnormality, the site may get one more bone marrow sample as soon as possible.

Bone marrow findings will be recorded and will be correlated with hematological samples.

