8.4.4 Evaluation of clonal evolution

Cytogenetic abnormalities will be assessed during the whole study. For all participants, regardless of disposition, the assessments will be monitored at Week 13, Week 26, Week 52 and yearly after, and when clinically indicated.

Cytogenetic abnormalities will be assessed by karyotyping (G-banding) and FISH (for example, probes targeting abnormalities in chromosome 3, 5, 7, 8 and those associated with SAA, MDS, AML etc).

Detection of PNH and measurement of PNH granulocyte clone size measurement by flow cytometry will be done at screening period. If persistently negative, it will be monitored every 6 months up to Year 2 (Week 104) and then Year 3 (Week 156) unless symptoms or signs develop. If the PNH screen is, or becomes positive, it will be tested every 3 months and only reduce the frequency if the proportion of the PNH cells has remained stable ([Killick et al 2016](#)).

Clonal evolution to AML and MDS will also be monitored during the study period, and relevant examinations will be done when clinically indicated.

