8.4.8 Appropriateness of safety measurements

The safety assessments selected are standard for this participant population.

Cytogenetic abnormalities, clonal evolution to PNH, evolution to MDS or AML will be evaluated in this study. A serious complication of aplastic anemia is its evolution to clonal hematologic diseases such as MDS and leukemia, which is usually associated with the appearance of a cytogenetic abnormality in bone marrow cells. The actuarial risk for this complication has been estimated in other studies at around 15% at 5 years. Conversion from normal to abnormal karyotype occurred at a constant rate after initial diagnosis, with about 50% of cases developing within the first 30 months ([Maciejewski et al 2002](#)). In CETB115AUS01T, clonal evolution occurred in 9 of 123 (7%) participants, which is within the range that would be expected with immunosuppression alone at 2 years after the initiation of treatment ([Townsley et al 2017](#)), while the estimated probability of being clonal evolution-free was above 90% up to 2 years. These data have since been updated by Novartis, and at the update cutoff of (28-Feb-2018), clonal evolution occurred in 15/154 (10%; vs. 7% at the original cutoff) which is consistent with the reported incidences of clonal evolution in SAA participant receiving first line treatment with IST alone (without the addition of eltrombopag). In the refractory AA patients treated with eltrombopag, evolution to an abnormal karyotype occurred in 16 (19%), and it is almost always an early event occurring within 6 months after initiation of eltrombopag ([Winkler et al 2019](#)).

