3. its duration (start and end dates) or if the event is ongoing, an outcome of not recovered/not resolved must be reported
4. whether it constitutes a SAE (see [Section 10.1.2](#) for definition of SAE) and which seriousness criteria have been met
5. action taken regarding with study treatment

All AEs must be treated appropriately. Treatment may include one or more of the following:

- Dose not changed
- Dose Reduced/increased
- Drug interrupted/withdrawn
- Its outcome

1. not recovered/not resolved;
2. recovered/resolved;
3. recovered/resolved with sequelae;
4. fatal; or unknown.

If the event worsens, the event should be reported a second time in the CRF noting the start date when the event worsens in toxicity. For grade 3 and 4 AEs only, if improvement to a lower

grade is determined a new entry for this event should be reported in the CRF noting the start date when the event improved from having been Grade 3 or Grade 4.

Conditions that were already present at the time of informed consent should be recorded in medical history of the participant.

AEs (including lab abnormalities that constitute AEs) should be described using a diagnosis whenever possible, rather than individual underlying signs and symptoms.

AE monitoring should be continued for at least 30 days following the last dose of eltrombopag.

Once an AE is detected, it must be followed until its resolution or until it is judged to be permanent (e.g. continuing at the end of the study), and assessment must be made at each visit (or more frequently, if necessary) of any changes in severity, the suspected relationship to the interventions required to treat it, and the outcome.

Information about adverse drug reactions for the investigational drug can be found in the eltrombopag Investigator's Brochure.

Abnormal laboratory values or test results constitute AEs only if they fulfill at least one of the following criteria:

- they induce clinical signs or symptoms
- they are considered clinically significant
- they require therapy

Clinically significant abnormal laboratory values or test results must be identified through a review of values outside of normal ranges/clinically notable ranges, significant changes from baseline or the previous visit, or values which are considered to be non-typical in participants with the underlying disease.

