10.1.3 SAE reporting

To ensure participant safety, every SAE, regardless of causality, occurring after the participant has provided informed consent and until 30 days following the last administration of eltrombopag must be reported to Novartis within 24 hours of learning of its occurrence. Detailed instructions regarding the submission process and requirements are to be found in the investigator folder provided to each site. SAEs occurring after the participant has provided informed consent until the time the participant is deemed a Screen Failure must be reported to Novartis.

All follow-up information for the SAE including information on complications, progression of the initial SAE and recurrent episodes must be reported as follow-up to the original episode within 24 hours of the investigator receiving the follow-up information. An SAE occurring at a different time interval or otherwise considered completely unrelated to a previously reported one must be reported separately as a new event. SAEs will be followed until resolution or until clinically relevant improvement or stabilization.

If the SAE is not previously documented in the Investigator's Brochure or Package Insert (new occurrence) and is thought to be related to the study treatment, a Chief Medical Office and Patient Safety (CMO&PS) Department associate may urgently require further information from the investigator for health authority reporting. Novartis may need to issue an investigator notification to inform all investigators involved in any study with the same study treatment that this SAE has been reported.

Suspected Unexpected Serious Adverse Reactions (SUSARs) will be collected and reported to the competent authorities and relevant Ethics Committees (EC) in accordance with European Union Guidance 2011/C 172/01 or as per national regulatory requirements in participating countries/regions.

Any SAEs experienced after the 30 day period following EOT (after eltrombopag discontinuation at anytime during the study) should only be reported to Novartis Safety if the investigator suspects a causal relationship to study treatment.

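### Clonal evolution is counted from AE-page terms alone, without reconciliation to karyotype, FISH and marrow results, and the plan does not settle whether events found after the on-treatment window count

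*SAP*

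**What the plan says.** **Source of the count.** SAP 2.12 and final SAP 2.11 carry the same sentence: "Cytogenetic abnormalities and clonal evolution will be selected from AE page in eCRF". Five labels are given (clonal evolution, cytogenetic abnormality, AML, MDS, PNH), and the share of participants with any such event goes into a summary table. Under SAP 2.8.4.3 in both versions, aspirate, biopsy, karyotype and FISH results are listed and nothing more.

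**Measurement.** On cytogenetics, protocol 8.4.4 says "For all participants, regardless of disposition, the assessments will be monitored at Week 13, Week 26, Week 52 and yearly after". On marrow aspirate and biopsy, 8.4.3 says these "will be sampled during Screening, Week 13, Week 26, Week 52 and yearly after". Follow-up for clonal evolution runs to Week 156 for all participants.

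**AE collection.** Protocol 10.1.1 says "AE monitoring should be continued for at least 30 days following the last dose of eltrombopag". The same section requires every new cytogenetic abnormality to be recorded as an AE. It adds that clonal evolution is to be tracked by SAE form plus eCRF if serious and by eCRF alone if not. Neither instruction carries a time limit. In Table 8-1 the "Adverse Events" row is marked from screening through the safety follow-up visit, with no mark under survival follow-up or Year 2 / Year 3. Under 10.1.3, SAEs arising more than 30 days after end of treatment "should only be reported to Novartis Safety if the investigator suspects a causal relationship to study treatment".

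**Analysis period.** SAP 2.8 in both versions limits safety tables and figures, deaths apart, to the on-treatment period, which closes 30 days after the last eltrombopag dose. The clonal sections speak of the study as a whole. Protocol 12.5.2 plans a summary at each planned assessment visit with an exact 95% interval; the SAPs plan only a rate.

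**The concern.** Clonal evolution is a secondary objective, and the protocol's risk section treats it as a harm to be watched. The study collects direct evidence for it on a fixed schedule in everyone, yet the analysis reads a secondary record: whether a site opened an AE page and whether the entry coded to one of five labels. That record has a scheduled life of eltrombopag plus 30 days, while the marrow schedule runs to Year 3.

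There are two separate ways to lose an event. It may never reach the AE page, or it may reach the page and then be dropped from the table because it started after the on-treatment window. Either loss works in one direction only. With 36 participants, one or two events move the reported rate visibly. The final analysis is the one exposed, since it is the one that takes in the Year 2 and Year 3 marrows.

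**Working it through.** **1. The plan's own figures.** The plan states no expected clonal rate for this study, so there is none to reproduce. The pivotal-study rates quoted in protocol 8.4.8 check: 15/154 = 9.7% (given as 10%) and 9/123 = 7.3% (given as 7%). The Clopper-Pearson routine used below returns SAP Table 3-1 exactly, for example 16/36: 27.9% to 61.9%.

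**2. AE window against marrow days.** Protocol Section 3 says "During the extension part, eltrombopag treatment will be provided up to Week 52", that is Day 365; non-responders stop at Week 26, Day 183. Marrow days in Table 8-1 are 92, 183, 365, 729 and 1093.
- Stop at Week 52: window ends 365 + 30 = Day 395. Marrows on Days 729 and 1093 lie outside. Uncovered follow-up: 1093 − 395 = 698 days, 698/1093 = 64%.
- Stop at Week 26: window ends 183 + 30 = Day 213. Marrows on Days 365, 729 and 1093 lie outside. Uncovered: 880/1093 = 81%. (Table 8-1 does mark AEs at Week 52, but that column belongs to the extension part, which non-responders do not enter.)

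These are shares of time, not shares of events.

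**3. Where the texts pull apart.**
- The 30 days in 10.1.1 are a minimum; the cytogenetic instruction there has no end; Table 8-1 has an end.
- The mandatory AE entry names cytogenetic abnormalities. MDS or AML seen on morphology is not named.
- 10.1.1 also says an abnormal test result is an AE only if it causes symptoms, is clinically significant or needs therapy. That sits badly with mandatory entry for abnormalities of unclear significance, which were 4 of the 15 cases in the pivotal study (protocol 4.5).
- SAP 2.8 would exclude an AE starting after the window; the clonal sections do not say that they override it. The one laboratory-based clonal summary, the GPI-negative cell shift table, also stops at the worst on-treatment value.

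**4. Scale, as an assumption.** Protocol 8.4.8 cites about 15% at 5 years at a constant rate. Rate: λ = −ln(0.85)/60 = 0.00271 per month. Expected events by month t: 36 × (1 − exp(−λt)). As a check, the model puts 52% of the 5-year cases within 30 months, against the protocol's "with about 50% of cases developing within the first 30 months".
- By Day 1093 (35.9 months): 3.34 events.
- By Day 395 (13.0 months): 1.24, so 2.09 come later (63%).
- By Day 213 (7.0 months): 0.68, so 2.66 come later (80%), if all stopped at Week 26.

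Events may cluster early. Scaling only the risk after Day 395, where p = 2.09/36 = 0.058 per person and the chance of at least one late event is 1 − (1 − share × p)^36:

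| Late risk as share of constant rate | Expected late events | Chance of at least one |
|---|---|---|
| 100% | 2.1 | 88% |
| 50% | 1.0 | 65% |
| 25% | 0.5 | 41% |
| 10% | 0.2 | 19% |

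**5. Effect on the reported rate.** Three events: 3/36 = 8.3% (1.8, 22.5). With two late events uncounted: 1/36 = 2.8% (0.1, 14.5).

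**The case against.** The strongest reply is that the AE page is where the protocol tells sites to put these findings. Entry of any new cytogenetic abnormality is compulsory and has no time limit, and the instruction to track all evidence of clonal evolution is broad enough to take in MDS and AML. Protocol 10.1.2 makes every malignant neoplasm serious. Section 9.1.1 has AEs and clonal assessments collected at abbreviated contacts after study treatment is discontinued, and 10.1.1 has AEs sought at each visit during the study. The causality condition in 10.1.3 governs reports to the safety department, not entry in the eCRF. Karyotype, FISH and marrow results are listed, so a missed case could be found by reading.

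Most of this stands. It rules out the stronger inference that late events will be lost, or that the rate is biased low against the 7% and 10% benchmarks. That would require sites not to follow 10.1.1, and the documents do not say how the benchmark events were ascertained. It also rules out taking two lost events as a forecast. Protocol 8.4.8 reports that evolution in refractory patients on eltrombopag came almost always within 6 months, and 4.5 reports that 6 of 7 chromosome 7 losses in treatment-naive patients came within 6.1 months.

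Three things are not answered. The abbreviated contacts follow discontinuation, which 9.1.1 defines as stopping before the planned duration, so they do not clearly reach someone who completes eltrombopag at Week 52. A correctly entered late AE can still be excluded under SAP 2.8. And a listing does not change the numerator.

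**Conclusion.** The point holds as a gap in the definition of the event and its time scope. Both SAPs rely on AE terms alone, with no derivation from or reconciliation to the direct evidence, and they do not settle whether an event after the on-treatment period counts. Events at the Year 2 and Year 3 marrows, and at Week 52 for those who stop at Week 26, may be missed or excluded. Late MDS or AML on morphology is the most exposed case; a late cytogenetic finding is better protected by 10.1.1. Any loss lowers the rate.

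The size is uncertain. About 2 late events of 3.3 is an upper scenario: it needs a constant rate, full follow-up of 36 participants, everyone treated to Week 52, and no late AE entries. With late risk at 10% to 50% of that rate, 0.2 to 1.0 late events are expected, and how many would go uncounted depends on site practice and on how SAP 2.8 is applied. A reader might take 64% or 81% as the proportion of events lost; those figures describe follow-up time outside the scheduled window only. This is a worthwhile, low-cost improvement to a safety summary. It does not affect the primary endpoint.

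**What to change.** In SAP 2.12 and final SAP 2.11:
- State that clonal events count through Year 3 whatever the on-treatment window, as an explicit exception to SAP 2.8.
- Define an event as a new clonal abnormality relative to baseline on karyotype or FISH, or MDS/AML on marrow morphology, at any scheduled or unscheduled sample, or a matching AE. For PNH, use flow cytometry or AE.
- Date the event by the sample.
- List disagreements between the two sources, as SAP 2.5.4 already does for complete response.
- Report abnormalities of unclear significance separately.
- Give the exact 95% interval from protocol 12.5.2, and record any remaining departure from that section in SAP Section 4, where neither version mentions it.

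The AE time scope in protocol 10.1.1 and Table 8-1 should also be reconciled.

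Cost: SAP wording and medical review of results that Table 8-1 already sends to the database, about 36 × 6 = 216 scheduled marrows if everyone attends. The real work is judging abnormalities of unclear significance, 4 of 15 (27%) in the pivotal study, which is why they need their own line. No dose, visit or treatment rule changes.

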- The risk specific to patients with SAA receiving eltrombopag is the potential for cytogenetic abnormalities. Clonal evolution is almost always an early event occurring within 6 months after initiation of eltrombopag in refractory SAA participants ([Winkler et al 2019](#)). The role of eltrombopag in the development of cytogenetic abnormalities in treatment-naïve SAA patients remains unknown. In Study CETB115AUS01T, clonal cytogenetic evolution occurred in 15/154 (10%) participants. Of the 15 participants who experienced cytogenetic abnormalities, 4 participants had chromosomal aberrations of unclear significance. 7 of these 15 participants had loss of chromosome 7, either alone or in combination with complex cytogenetic abnormalities, and in 6 of them, it occurred within the first 6.1 months. In 3 of the 7 participants this was accompanied by morphologic evidence of dysplasia or full myeloid malignant transformation. In 3 of 15 participants deletion of chromosome 13 was reported, considered to be a good prognostic factor in patients with aplastic anemia. One participant had a follow-up bone marrow assessment at 5 years which was markedly changed compared to prior bone marrow assessment, with features of dysplasia with hypercellularity concerning for potential development of myelodysplastic syndrome (MDS). It is unclear if these evolutions occurred due to the underlying disease, the IST and/or eltrombopag. In Study CETB115E1202, one cytogenetic abnormality was detected and it was not associated with dysplasia and increase in bone marrow blasts; no progression to MDS was reported. For the proposed protocol, bone marrow examination including cytogenetics will be performed at Week 13, Week 26, Week 52 and yearly after, as

described in [Section 8.4.3](#) and [Table 8-1](#). Development of new cytogenetic abnormalities must be documented and will result in permanent discontinuation of study treatment as described in [Section 9.1.1](#).

- There may be unforeseen risks with the study treatment which could be serious. These include but may not be limited to drug to drug interactions and long-term safety. Close adherence to eligibility criteria, study procedures safety monitoring and dose adjustment will help to minimize unforeseen risks. Potential for drug-drug interaction and measures to minimize undesired drug-drug interactions are described in [Section 6.2.1](#) and [Section 6.2.2](#).

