- Listing of all laboratory data with values flagged to show the corresponding CTCAE grades if applicable and the classifications relative to the laboratory normal ranges

For laboratory tests where grades are defined by CTCAE:

- Worst post-baseline CTCAE grade (regardless of the baseline status). Each participant will be counted only once for the worst grade observed post-baseline.
- Shift tables using CTCAE grades to compare baseline to the worst on-treatment value.

For laboratory tests where grades are not defined by CTCAE:

- Shift tables using the low/normal/high/ (low and high) classification to compare baseline to the worst on-treatment value.

In addition, regardless of the transfusion or G-CSF, laboratory tests (Platelet counts, Hemoglobin, Neutrophil count) value and change from baseline will be listed and summarized in scheduled visits using descriptive statistics (mean, SD, median, interquartile range, and range).

Cytogenetic abnormalities, clonal evolution to PNH and clonal evolution to AML or MDS

Cytogenetic abnormalities, clonal evolution to PNH, evolution to MDS or AML will be summarized at each planned biomarker assessment visit. The number and percentage of participants with above clonal evolutions will be presented and exact 95% confidence interval will be reported. If sufficient data are available, the time to clonal cytogenetic abnormalities, clonal evolution to PNH, AML or MDS until data cutoff may also be estimated using Kaplan-Meier method and will be plotted.

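### The SAPs commit to one clonal-evolution rate that includes PNH and has no confidence interval, so it is not like for like with the protocol's cytogenetic figure of 15/154

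*SAP*

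**What the plan says.** Clonal evolution is a secondary objective. Protocol 12.5.2 states: "Cytogenetic abnormalities, clonal evolution to PNH, evolution to MDS or AML will be summarized at each planned biomarker assessment visit". It then promises the number and percentage of participants with these evolutions and an exact 95% confidence interval.

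SAP 2.12 (primary analysis) and SAP 2.11 (final analysis) select events from the AE page using the terms "clonal evolution / cytogenetic abnormality / AML / MDS / PNH". Both then commit to one summary: "the rate of the subjects who developed any clonal evolution (e.g., clonal evolution to PNH, evolution to AML or MDS etc.) will be calculated". Neither mentions a confidence interval or component rates. Both add short narratives and a listing for participants with new cytogenetic abnormalities. Section 4 of each SAP, on changes to protocol-specified analyses, lists only added efficacy endpoints.

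The reference figure is in Protocol 4.5: "In Study CETB115AUS01T, clonal cytogenetic evolution occurred in 15/154 (10%) participants". Protocol 8.4.8 repeats the same 15/154 under the broader label of clonal evolution and describes it as a figure "which is consistent with the reported incidences of clonal evolution in SAA participant receiving first line treatment with IST alone". That section opens by listing PNH among the events evaluated in this study.

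**The concern.** The protocol uses one label, clonal evolution, for two different counts. In the pivotal-study figure it means cytogenetic change. In the SAPs it means cytogenetic change, MDS, AML or PNH. A reader of the study report will naturally set the new rate beside the 10% that the protocol itself quotes.

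Protocol 4.5 names cytogenetic abnormality as the risk specific to SAA patients receiving eltrombopag. A pooled rate can sit above 10% because of PNH alone. It can also look unremarkable while its cytogenetic or MDS/AML share is high. In either case the one summary rate the SAPs commit to does not report the risk the protocol singles out, and it comes without the interval the protocol promised.

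**Working it through.** **1. The plan's own figures.** 15/154 = 9.74%, which rounds to the stated 10%; the exact (Clopper-Pearson) 95% CI is 5.6% to 15.6%. The original cutoff in Protocol 8.4.8, 9/123 = 7.32%, rounds to the stated 7%. The interval is Beta(0.025; x, n−x+1) to Beta(0.975; x+1, n−x) quantiles. The same routine reproduces SAP Table 3-1: 14/36 (23.1, 56.5), 16/36 (27.9, 61.9), 18/36 (32.9, 67.1).

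**2. What the 15 were.** Protocol 4.5 states: "Of the 15 participants who experienced cytogenetic abnormalities, 4 participants had chromosomal aberrations of unclear significance". It continues: "7 of these 15 participants had loss of chromosome 7, either alone or in combination with complex cytogenetic abnormalities". Three had deletion of chromosome 13, and one participant had a markedly changed marrow at 5 years that raised concern for MDS. Read as separate groups, 4 + 7 + 3 + 1 = 15. No PNH case is mentioned. MDS/AML features are not absent: 3 of the 7 chromosome 7 cases also had dysplasia or malignant transformation.

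**3. Effect of adding PNH, without assuming a rate.** At the pivotal rate, 36 × 0.0974 = 3.5 participants would be expected to have cytogenetic events. Take 3 of 36 and add two with PNH only:

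- 3/36 = 8.3% (exact 95% CI 1.8 to 22.5)
- 5/36 = 13.9% (exact 95% CI 4.7 to 29.5)

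The cytogenetic count is the same in both rows.

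**4. Range under assumed PNH rates.** The documents give no PNH incidence, so the rate q is an assumption, as is independence of PNH and cytogenetic events. Pooled rate = 1 − (1 − 0.0974)(1 − q).

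- q = 3%: 12.4%
- q = 5%: 14.3%
- q = 10%: 18.8%
- q = 20%: 27.8%

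The smallest count whose exact lower limit lies above 9.74% is 8/36 (10.1%; 7/36 gives 8.2%). The chance of 8 or more is 2.0% with no PNH, 7% at q = 3%, 13% at q = 5% and 36% at q = 10%. This threshold is a yardstick for size only; the plan contains no such rule.

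**5. Do other planned tables supply the components?**

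- AE tables by preferred term cover the on-treatment period, which ends 30 days after the last eltrombopag dose. Eltrombopag is provided only to Week 52, while clonal evolution is followed to Year 3.
- Karyotype, FISH and marrow results are listings.
- The GPI-negative cell table is an on-treatment shift table split at 50%.

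None commits to a whole-study cytogenetic rate.

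**The case against.** The strongest reply is that nothing in the plan compares this study with 10%. Protocol 4.5 is background, and Protocol 8.4.8 compares the pivotal study, not this one, with immunosuppression alone. The study follows an estimation strategy. This stands: no planned inference is affected.

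A reader might infer that scheduled PNH flow cytometry would feed every small clone into the rate. The documents do not support that. The rate is drawn from the AE page. Under Protocol 10.1.1 a test result is an AE only if it causes signs or symptoms, is clinically significant or needs therapy. Any new cytogenetic abnormality must be recorded as an AE, but there is no matching rule for a PNH clone. The PNH contribution could therefore be small.

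A reader might also infer that the components cannot be separated at all. With about 36 participants, the narratives, the cytogenetic listings and the flagged AE listings allow it person by person. The SAPs do not withdraw Protocol 12.5.2, and a summary table could carry component rows. What remains is that neither SAP commits to those rows or to the interval.

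**Conclusion.** The point holds as a mismatch of event type and as a loss of detail between Protocol 12.5.2 and both SAPs. In the illustration, two PNH-only participants raise the reported rate by 5.6 percentage points (13.9 − 8.3) with cytogenetic evolution unchanged. The real size is unknown because it depends on how many PNH events reach the AE page.

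Two stronger readings should be avoided. The first is that pooling will produce a false safety signal with a stated probability: the probabilities above rest on an assumed PNH rate and on a threshold that is not in the plan, and they treat 9.74% as fixed although its own interval is 5.6% to 15.6%. The second is that cytogenetic abnormality or MDS/AML together form the definition behind 15/154: Protocol 4.5 does not show that MDS or AML without a cytogenetic abnormality would have counted.

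Matching the event type does not make the two studies fully comparable. The pivotal count appears to include one participant assessed at 5 years, whereas this study ends at Year 3. The harm is confined to interpretation of the summary rate, but it concerns a named risk and is easily avoided.

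**What to change.** In SAP 2.12 and final-analysis SAP 2.11, replace the single rate with whole-study numbers, percentages and exact 95% CIs for:

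- (a) new cytogenetic abnormality;
- (b) evolution to MDS or AML;
- (c) evolution to PNH;
- any clonal evolution, kept as an additional row.

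Add one sentence saying that only row (a) is like for like in event type with 15/154, and that follow-up differs. The cost is a few table rows from data already collected. Intervals will be wide at N = 36, as 3/36 (1.8 to 22.5) shows.
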